The risk of preventive interventions for early OHSS and/or early OHSS is related to the ovarian response potential. AMH is a well-established predictor of ovarian response to gonadotropin treatment and was confirmed to be the best endocrine marker of ovarian response to FE 999049 treatment in the phase 2 trial.

For each endpoint two different logistic regression models will be fitted assuming an increasing risk with increasing AMH as follows:

$$\text{LOGIT}(\pi) = \beta_0 + \beta_1 \log(\text{AMH}),$$

where π denotes the risk and the β 's denotes the regression coefficients.

A comparison of the two treatment regimens with respect to the risk will be performed by adding treatment group as factor and the interaction term between treatment group and $\log(\text{AMH})$ to the model as follows:

$$\text{LOGIT}(\pi) = \beta_0 + \beta_1 \text{Treatment} + \beta_2 \log(\text{AMH}) + \beta_3 \text{Treatment} * \log(\text{AMH})$$

The two models will be compared using the likelihood ratio test. Adjusted odds ratio estimates (comparing FE 999049 to FOLLISTIM) and associated 95% Wald CI will be provided.

The adequacy of the model fits will be evaluated using the Hosmer-Lemeshow goodness-of-fit test. The estimated risks based on the models will be plotted as a function of AMH, i.e. overall and for each treatment group.

Late OHSS (Including OHSS of Moderate/Severe Grade)

OHSS will for each treatment group be tabulated by classification (mild, moderate, severe, moderate and severe) and grade (1, 2, 3, 4, 5). Late OHSS is defined as OHSS with onset > 9 days after triggering of final follicular maturation.

This endpoint will be tabulated and analysed in a similar manner as the proportion of subjects with early OHSS. The analysis will be performed for subjects with late OHSS, and subjects with late OHSS of moderate or severe grade.

OHSS (Early and/or Late) and/or Preventive Interventions for Early OHSS

This endpoint will be tabulated and analysed in a similar manner as the proportion of subjects with early OHSS and/or preventive interventions for early OHSS. Analyses will be performed for subjects with early and/or late OHSS, subjects with early and/or late OHSS of moderate or severe grade, subjects with early and/or late OHSS and/or preventive interventions for early OHSS, and subjects with early and/or late OHSS of moderate or severe grade and/or preventive interventions for early OHSS.

Number and Size of Follicles during Stimulation

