10.3 OHSS

Early OHSS (Including OHSS of Moderate/Severe Grade) and/or Preventive Interventions for Early OHSS

OHSS will for each treatment group be tabulated by classification (mild, moderate, severe, moderate or severe) and grade (1, 2, 3, 4, 5). Early OHSS is defined as OHSS with onset ≤ 9 days after triggering of final follicular maturation. Note this includes OHSS with onset before triggering and OHSS with onset during stimulation where triggering is not performed.

This endpoint will be tabulated and analysed in a similar manner as the proportion of subjects with cycle cancellation, i.e. using a logistic regression model with treatment and AMH stratum as fixed factors. Analyses will be performed for subjects with early OHSS, subjects with early OHSS of moderate or severe grade, subjects with preventive interventions for early OHSS, subjects with early OHSS and/or preventive interventions for early OHSS, and subjects with early OHSS of moderate or severe grade and/or preventive interventions for early OHSS. The difference between treatments will be reported as an odds ratio including a 95% confidence interval and a p-value for the test of no difference between treatments.

The risk of preventive interventions for early OHSS and/or early OHSS is related to the ovarian response potential. AMH is a well-established predictor of ovarian response to gonadotropin treatment and was confirmed to be the best endocrine marker of ovarian response to FE 999049 treatment in the phase 2 trial. Since FE 999049 is dosed based on AMH it is likely that the relationship between AMH and the risk of experiencing preventive interventions for early OHSS and/or early OHSS differs between FE 999049 and FOLLISTIM. To further explore this for each of the endpoints above, two different logistic regression models will be fitted assuming an increasing risk with increasing AMH with two nested models as follows:

Model 1: $\text{LOGIT}(\pi) = \beta_0 + \beta_1 \cdot \ln(\text{AMH})$,

where π denotes the risk and the β 's denotes the regression coefficients.

Model 2: $\text{LOGIT}(\pi) = \beta_0 + \beta_1 \cdot \ln(\text{AMH}) + \beta_{2,i} + \beta_{3,i} \cdot \ln(\text{AMH})$, where $i=1, 2$ indicates the two treatments. This is model 1 with addition of treatment and treatment-by- $\ln(\text{AMH})$ interaction terms.

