The two models will be compared using the likelihood ratio test. Adjusted odds ratio estimates (comparing FE 999049 to FOLLISTIM) and associated 95% Wald CI will be provided. A statistically significant improvement with model 2 compared to model 1 should be interpreted as a treatment difference in that the relationship between AMH and the risk of experiencing preventive interventions for early OHSS and/or early OHSS.

The estimated risks based on the models will be plotted as a function of AMH, i.e. overall and for each treatment group. The plots will include observed incidences for AMH-based subgroups of

subjects. The adequacy of the model fits will be evaluated using the Hosmer-Lemeshow goodness-of-fit test and by examining how well the model fit describes the data in the plot.

It can be noted that the likelihood ratio test using two nested models above corresponds to a test of the contrast $\beta_{2,1} = \beta_{2,2} = \beta_{3,1} = \beta_{3,2} = 0$ in model 2 above.

Late OHSS (Including OHSS of Moderate/Severe Grade)

OHSS will for each treatment group be tabulated by classification (mild, moderate, severe, moderate and severe) and grade (1, 2, 3, 4, 5). Late OHSS is defined as OHSS with onset >9 days after triggering of final follicular maturation.

This endpoint will be tabulated and analysed in a similar manner as the proportion of subjects with early OHSS. The analysis will be performed for subjects with late OHSS, and subjects with late OHSS of moderate or severe grade.

OHSS (Early and/or Late) and/or Preventive Interventions for Early OHSS

This endpoint will be tabulated and analysed in a similar manner as the proportion of subjects with early OHSS and/or preventive interventions for early OHSS. Analyses will be performed for subjects with early and/or late OHSS, subjects with early and/or late OHSS of moderate or severe grade, subjects with early and/or late OHSS and/or preventive interventions for early OHSS, and subjects with early and/or late OHSS of moderate or severe grade and/or preventive interventions for early OHSS.

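### SAP 10.3 reads a joint test of treatment and treatment-by-ln(AMH) as showing a different AMH–OHSS relationship between arms, but a constant shift in risk also makes that test significant

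*SAP*

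**What the plan says.** SAP 10.3 gives the motive for the nested models: "Since FE 999049 is dosed based on AMH it is likely that the relationship between AMH and the risk" of OHSS or its prevention differs between the arms. Model 1 contains ln(AMH) only. Of Model 2 the SAP says "This is model 1 with addition of treatment" together with the treatment-by-ln(AMH) interaction. The two are compared by a likelihood ratio test for each of five early-OHSS endpoints. The late and combined endpoints are to be analysed in a similar manner.

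The SAP then fixes the reading of a significant result: "A statistically significant improvement with model 2 compared to model 1 should be interpreted as a treatment difference in that the relationship between AMH", with OHSS risk or its prevention as the other term. The sentence is grammatically broken, but its subject is the AMH–risk relationship. Shortly afterwards the same section writes: "It can be noted that the likelihood ratio test using two nested models above corresponds to a test of the contrast", in which β2,1 = β2,2 = β3,1 = β3,2 = 0.

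Protocol 9.7.4 describes the same comparison more neutrally: "A comparison of the two treatment regimens with respect to the risk will be performed by adding treatment group as factor" plus the interaction. It does not say that a significant result concerns the relationship with AMH.

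**The concern.** The question SAP 10.3 poses is one of effect modification: does dosing on AMH change how OHSS risk depends on AMH? The test answers a wider question, whether there is any treatment difference in risk at given AMH. If FE 999049 lowers the odds of OHSS by the same factor at every AMH level, the slopes are equal, yet the test has power to reject. Under the stated rule that result would be reported as a difference in the AMH–risk relationship.

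No unconditional test of the interaction in the ln(AMH) model is planned, so nothing in the SAP formally separates the two explanations. The protocol presents a safer OHSS profile as a clear need in Japan, and an overall reduction in OHSS is plausible. That is the situation in which the rule would support an effect-modification statement the test has not earned.

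**Working it through.** **What the test tests.** With two arms, Model 2 gives a between-arm difference in log-odds at a given AMH of

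(β2,1 − β2,2) + (β3,1 − β3,2)·ln(AMH).

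Only these two differences are identifiable, so Model 2 against Model 1 is a 2-df test that both are zero. A constant odds ratio (OR) means β2,1 − β2,2 = ln(OR) ≠ 0 and β3,1 − β3,2 = 0. The joint null is then false although the slopes are equal.

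**Inputs from the documents.**
- Sample size (SAP 3.2): 155 per group gives 90% power for a margin of −3.0 oocytes and SD 8.1. Recalculation with the noncentral t gives 90.15% at 155. Allowing 5% for major deviations, 155/0.95 = 163.2, rounded up to 164 per arm, or 328. The plan's figure is reproduced. It gives no figure for the likelihood ratio test.
- FOLLISTIM risk (Protocol 1.1): 19.5% early moderate/severe OHSS in the Japanese phase 2 trial. Reported Japanese OHSS rates range from 5% to 28.3%.
- Overseas rates, FE 999049 against follitropin alfa (Protocol 1.1):
  - 4.7% vs 6.2%: OR = (0.047/0.953)/(0.062/0.938) = 0.75
  - 4.4% vs 6.5%: OR = (0.044/0.956)/(0.065/0.935) = 0.66
  - 3.3% vs 5.6%: OR = (0.033/0.967)/(0.056/0.944) = 0.58
- Test level 5% (Protocol 9.7.1).

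**Assumptions not in the documents.** ln(AMH) is normal with SD 0.7, and the slope is 1. The constant ORs of 0.5 and 0.4 are illustrative. Applying overseas ORs to a Japanese control risk is also an assumption.

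**Calculation.** Data follow logit(π) = a + ln(AMH) + ln(OR)·treatment, with no interaction and with a set so that the FOLLISTIM group incidence is 19.5%. The large-sample noncentrality is λ = 2[ℓ(Model 2) − ℓ(Model 1)] at expected counts, and rejection is P(χ²₂(λ) > 5.991). Simulation used 3,000 trials per setting.

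| Constant OR | λ | 2-df test, large sample | 2-df test, simulated | Interaction only (1 df), simulated |
|---|---|---|---|---|
| 1.00 | 0 | 5% | 5% | 5% |
| 0.75 | 0.94 | 13% | 14% | 6% |
| 0.66 | 1.81 | 21% | 20% | 6% |
| 0.58 | 3.10 | 33% | 32% | 5% |
| 0.50 | 4.66 | 47% | 48% | 5% |
| 0.40 | 7.54 | 69% | 72% | 6% |

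The noncentrality of the interaction test is exactly zero in every row. Repeat runs differ by a few points. Setting 19.5% at median AMH instead of as the group incidence gives 36% at 0.58, 51% at 0.50 and 73% at 0.40.

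**Sensitivity.**
- At OR 0.4, the large-sample rejection rate is 24% with a 5% FOLLISTIM risk and 82% with 28.3%.
- At ORs 0.75–0.58 with a 5% risk it is only 7–13%.
- Slopes of 0.5 or 1.5 and an ln(AMH) SD of 0.5 or 0.9 change little. At OR 0.4 the two SDs give 71% and 69%.
- At 19.5% risk and slope 1, among significant 2-df results for ORs 0.6 to 0.3, only 6–15% also had a significant interaction.

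**The case against.** The strongest reply is that the SAP says relationship, not slope. If the word means the whole risk curve, two parallel curves on the logit scale also differ, and a joint test of intercept and slope is the standard test that two curves coincide. The protocol's neutral wording and the planned plots by treatment group fit that reading. The SAP also prints the joint contrast, so it conceals nothing. On this view the rejections tabulated above are correct, not false positives.

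Much of this stands. The test is valid for any treatment difference given AMH, and the percentages are errors only if the result is reported as effect modification. But the reason SAP 10.3 gives, that FE 999049 is dosed on AMH, points to effect modification, and the broken sentence does not settle the matter.

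The plan also covers effect modification in part. The cycle-cancellation method that SAP 10.3 borrows (SAP 9.4) looks at a treatment-by-AMH interaction if both factors are significant, and the plots show observed incidences for AMH subgroups. The first is conditional and uses two strata, and the second is descriptive. Neither replaces an interaction test in the ln(AMH) model.

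A reader might infer that the joint test also costs power to detect a plain treatment effect. The documents do not support that. SAP 10.3 already plans a logistic model with treatment and AMH stratum for each early-OHSS endpoint, giving a 1-df treatment test. At OR 0.5 its power is about 61%, against 63% when adjusting for ln(AMH) itself.

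**Conclusion.** The test and its stated reading do not match. A significant Model 2 against Model 1 result shows some treatment difference in OHSS risk at given AMH. It does not by itself show that risk depends on AMH differently in the two arms.

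The size depends on assumptions. With about 20% FOLLISTIM risk and no interaction, the joint test rejects in about 14–35% of trials at the ORs implied by the overseas rates, and in about 50–71% at the assumed ORs of 0.5–0.4. The frequencies fall sharply for rarer endpoints. The mismatch follows from the model structure and does not depend on the assumed AMH distribution or slope.

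A reader might go further and infer that the test is invalid, that it is always significant under a constant shift, or that the trial's main claim is at risk. None of these follows. The joint null is stated correctly, rejection depends on OR and event rate, and the analysis is exploratory and separate from the non-inferiority conclusion on oocytes. The point is a worthwhile correction of limited consequence.

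**What to change.** 1. Reword the interpretation sentence in SAP 10.3 so that a significant Model 2 against Model 1 result means some treatment difference in risk given AMH.
2. Add an intermediate model with treatment and ln(AMH) but no interaction. Base any statement that the AMH–risk relationship differs on the 1-df likelihood ratio test of Model 2 against it, and report the between-arm slope difference (β3,1 − β3,2) with its 95% CI.
3. Keep the treatment and AMH-stratum model as the test of the overall treatment effect.

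The cost is a reworded sentence, an added one, and one extra logistic fit per endpoint: five early-OHSS endpoints, or eleven (5 + 2 + 4) if the exploration carries over to the late and combined ones. No new data are needed.

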10.4 Injection Site Reactions to IMP

For each injection site reaction (redness, pain, itching, swelling and bruising), the number of events and number of subjects experiencing those events will be tabulated by time (immediately, 30 minutes, 24 hours), reaction and intensity (none, mild, moderate and severe).

10.5 Pen Malfunction

The frequency of technical malfunctions of the administration pens will be tabulated.

10.6 Safety Laboratory Variables

Safety laboratory variables will be grouped under “Haematology” and “Clinical Chemistry”.

The baseline is based on the blood sample drawn at screening. Treatment-emergent laboratory data will be obtained at end-of-stimulation and end-of-trial.

10.6.1 Summary Statistics

The circulating levels of clinical chemistry and haematology parameters including change from baseline will be tabulated for each time-point for each laboratory variable.

10.6.2 Laboratory Variable Changes Relative to Normal Range

Shift tables will be prepared to compare baseline values to the end-of-stimulation and end-of-trial values, using a categorisation of low, normal and high values at each visit. Low, normal and high will be defined according to the reference ranges provided by the central laboratory.

10.6.3 Markedly Abnormal Changes

For each laboratory variable, a summary table will be prepared displaying the proportion of subjects who have at least one markedly abnormal value. The table will also include a break-down by classification of the baseline value. Markedly abnormal criteria for the safety laboratory variables is specified in [Appendix 1](#).

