Shift tables will be prepared to compare baseline values to the end-of-stimulation and end-of-trial values, using a categorisation of low, normal and high values at each visit. Low, normal and high will be defined according to the reference ranges provided by the central laboratory.

For each laboratory variable, a summary table will be prepared displaying the proportion of subjects who have at least one markedly abnormal value. The table will also include a break-down by classification of the baseline value. Markedly abnormal criteria for the safety laboratory variables will be specified in the SAP.

All laboratory values will be listed by subject number and time point. Values outside the reference range and markedly abnormal values will be flagged.

Injection Site Reactions to IMP

For each injection site reaction (redness, pain, itching, swelling and bruising), the number of events and number of subjects experiencing those events will be tabulated by time (immediately, 30 minutes, 24 hours), reaction and intensity (none, mild, moderate and severe).

Pen Malfunction

The frequency of technical malfunctions of the administration pens will be tabulated.

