- Implantation rate (number of gestational sacs 5-6 weeks after transfer divided by number of blastocysts transferred)
- Proportion of subjects with cycle cancellation due to poor or excessive ovarian response or blastocyst transfer cancellation due to excessive ovarian response / OHSS risk
- Proportion of subjects with <4, 4-7, 8-14, 15-19 and ≥ 20 oocytes retrieved
- Proportion of subjects with extreme ovarian responses, defined as <4, ≥ 15 or ≥ 20 oocytes retrieved
- Proportion of subjects with preventive interventions for early OHSS
- Proportion of subjects with early OHSS (including OHSS of moderate/severe grade) and/or preventive interventions for early OHSS

- Proportion of subjects with late OHSS (including OHSS of moderate/severe grade)
- Proportion of subjects with OHSS (early and/or late) and/or preventive interventions for early OHSS
- Number and size of follicles on stimulation day 6 and end-of-stimulation
- Fertilisation rate as well as number and quality of embryos on day 3 and blastocysts on day 5 after oocyte retrieval
- Circulating concentrations of FSH, LH, estradiol, progesterone, inhibin A and inhibin B on stimulation day 6 and end-of-stimulation
- Total gonadotropin dose and number of stimulation days
- Frequency and intensity of adverse events
- Changes in circulating levels of clinical chemistry and haematology parameters and proportion of subjects with markedly abnormal changes
- Frequency and intensity of injection site reactions (redness, pain, itching, swelling and bruising) assessed by the subject during the stimulation period
- Technical malfunctions of the administration pens

Pregnancy Follow-up Information

- Ongoing pregnancy rate (at least one intrauterine viable fetus 10-11 weeks after transfer) and live birth rate
- Neonatal health at birth and at 4 weeks after birth

3 Trial Design

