Appendix 1 Markedly Abnormal Laboratory Values and Vital Signs

Table 1: Markedly Abnormal Criteria for Haematology

Variable	Units	Markedly abnormal criteria	
		Low	High
Haemoglobin	g/L	≤ 115	Not applicable
Haematocrit	Ratio	≤ 0.37	≥ 0.56
Total WBC	10 ⁹ /L	≤ 2.8	≥ 16.0
Eosinophils	%	Not applicable	≥ 10
Neutrophils	%	≤ 15	≥ 90
Lymphocytes	%	≤ 10	≥ 80
Monocytes	%	Not applicable	≥ 20
Basophils	%	Not applicable	≥ 5
Bands	%	Not applicable	≥ 20
Platelets	10 ⁹ /L	≤ 75	≥ 700
Total RBC	10 ¹² /L	≤ 3.5	Not applicable

RBC: Red blood cells, WBC: White blood cells

Table 2: Markedly Abnormal Criteria for Clinical Chemistry (including Coagulation)

Variable	Units	Markedly abnormal criteria	
		Low	High
Albumin	g/L	< 20	Not applicable
ALT	IU/L	Not applicable	> 3xULN
Alkaline phosphatase	IU/L	Not applicable	> 3xULN
AST	IU/L	Not applicable	> 3xULN
Bicarbonate	mmol/L	< 15.1	> 34.9
Bilirubin direct	umol/L	Not applicable	> 2xULN
Bilirubin total	umol/L	Not applicable	> 2xULN
Blood urea nitrogen	mmol/L	Not applicable	> 12.5
Calcium	mmol/L	< 1.75	> 2.74
Chloride	mmol/L	Not applicable	Not applicable
Cholesterol (30-40Y)	mmol/L	Not applicable	> 10.34
Creatinine	umol/L	Not applicable	> 3xULN
GGT	IU/L	Not applicable	> 3xULN
Glucose	mmol/L	< 2.5	> 16.7
LDH	IU/L	Not applicable	> 3xULN
Phosphate	mmol/L	< 0.6	Not applicable
Potassium	mmol/L	< 3.0	> 5.8
Sodium	mmol/L	< 125	> 155
Total protein	g/L	< 20	> 90
Uric acid	umol/L	Not applicable	> 595

MCV: Mean corpuscular volume, MCH: Mean corpuscular haemoglobin, MCHC: Mean corpuscular haemoglobin concentration, ALT: Alanine Aminotransferase, AST: Aspartate Aminotransferase, GGT: Gamma Glutamyl Transferase, LDH: Lactate Dehydrogenase.

Table 3: Markedly Abnormal Criteria for Endocrine Parameters

Variable	Units	Markedly abnormal criteria (High)
LH	IU/L	> 10
Progesterone	nmol/L	> 3.18
LH surge	Not applicable	LH > 10 IU/L and Progesterone > 3.18 nmol/L on the same day

LH: Luteinizing Hormone

Table 4: Reference Ranges and Markedly Abnormal Criteria for Vital Signs

Variable	Reference range		Markedly abnormal criteria	
	Low	High	Low	High
Systolic blood pressure (mmHg)	<90	>140	< 80 and decrease of ≥ 20 from baseline	> 155 and increase of ≥ 20 from baseline
Diastolic blood pressure (mmHg)	<60	>90	< 50 and decrease of ≥ 15 from baseline	> 100 and increase of ≥ 15 from baseline
Pulse rate (bmp)	<50	>100	< 45 and decrease of ≥ 15 from baseline	> 130 and increase of ≥ 15 from baseline

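### The laboratory endpoint is named for markedly abnormal changes but counts markedly abnormal values, so women already beyond a limit at screening and unchanged enter the headline proportion

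*SAP*

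**What the plan says.** The endpoint in SAP section 2, worded identically in protocol 2.2, has two parts: "Changes in circulating levels of clinical chemistry and haematology parameters and proportion of subjects with markedly abnormal changes". SAP 10.6.3 also has markedly abnormal changes as its heading.

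The counting rule differs. SAP 10.6.3 plans a table of the "proportion of subjects who have at least one markedly abnormal value", and protocol 9.7.4 has the same rule: a table "displaying the proportion of subjects who have at least one markedly abnormal value". Both go straight on to a partial safeguard: "The table will also include a break-down by classification of the baseline value".

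On timing, SAP 10.6 says "The baseline is based on the blood sample drawn at screening" and "Treatment-emergent laboratory data will be obtained at end-of-stimulation and end-of-trial". SAP 10.6.3 does not itself restrict the count to post-baseline samples; that has to be read across from 10.6.

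The limits are in SAP Appendix 1. Tables 1 and 2 give laboratory limits as fixed levels (haemoglobin ≤ 115 g/L, haematocrit ≤ 0.37) or ULN multiples (ALT > 3xULN). None refers to baseline. Table 4, for vital signs, does; low systolic pressure, for example, is "< 80 and decrease of ≥ 20 from baseline".

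**The concern.** A proportion with markedly abnormal changes should tell the reader how many women moved into an abnormal range after starting treatment. The rule as written adds women who were there already. Take a woman with haemoglobin 112 g/L at screening, 113 at end-of-stimulation and 112 at end-of-trial. Nothing has changed, yet she counts under a heading that says something did.

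Entry criteria do not rule this out. Exclusion criterion 12 (protocol 4.1.2) leaves the clinical relevance of a screening abnormality to the investigator's judgement and does not refer to the Appendix 1 limits. It may lower the number affected, by an unknown amount.

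At stake is how one of the two parts of the laboratory endpoint is read: the absolute rate of change is overstated in both arms, and a ratio between arms is pulled towards 1.

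**Working it through.** The documents give no figure for this endpoint, so there is nothing to reproduce. The rule follows from the text; its size needs assumed distributions.

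**1. The rule.** Endpoint name: change. Counting rule: value. Laboratory criteria: level only. Vital-sign criteria: level and change. A woman who meets a laboratory criterion at screening and again later therefore satisfies the rule whatever her change.

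**2. Does the break-down separate her?** SAP 10.6.3 does not define the baseline classes. The only laboratory classification described is low/normal/high by central laboratory reference range (SAP 10.6.2). If that is meant, there are two cases:
- Limit at or outside the reference range: women already beyond it all fall in the low or high row, so the normal row holds new crossings only. The low or high row still mixes women beyond the limit with women short of it.
- Limit inside the reference range: some women already beyond it are classed as normal.

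The reference ranges are not in the documents, so one cannot tell which case applies to which variable. The shift tables use the same ranges, so they do not give the number of new crossings of the markedly abnormal limit either.

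**3. Size for haemoglobin (assumed inputs).** Limit L = 115 g/L (Appendix 1). Assumed: mean m = 128, total SD σ = 10, within-woman SD s = 5, one screening and two later samples, no drug effect. The true level T is normal with mean m and variance σ² − s² = 75. The chance that one sample meets the criterion is p(T) = Φ((L − T)/s). Averaging over T:
- Beyond the limit at screening: Φ((115 − 128)/10) = Φ(−1.3) = 9.7%.
- Flagged by the rule: E[1 − (1 − p)²] = 14.4%, or 164 × 0.144 ≈ 24 women per arm.
- Flagged and already beyond at screening: E[p{1 − (1 − p)²}] = 6.5%, or about 11 per arm. Share of flags: 6.5/14.4 = 45%.
- Newly beyond: 14.4 − 6.5 = 7.9%. Among women not beyond at screening: 7.9/(100 − 9.7) = 8.8%.

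Over means 125 to 132, SD 9 to 11 and within-woman SD 4 to 6, the no-effect flag rate runs from 4.6% to 26.3%. The pre-existing share runs from 21% (1.08/5.21; mean 132, SD 9, within-woman SD 6) to 64% (15.0/23.6; mean 125, SD 11, within-woman SD 4).

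**4. Haematocrit ≤ 0.37.** With assumed means 0.385 to 0.405, SD 0.025 to 0.03 and within-woman SD 0.015, 13% to 41% are flagged, of whom 35% to 61% were already beyond the limit.

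**5. Effect on a comparison.** Let b be the share of women beyond the limit at screening and still beyond it on trial, and i the rate of new crossings among the rest. The headline proportion is b + (1 − b)i. For a true i of 10% against 5% (ratio 2.0, difference 5.0 points):

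| b | Headline proportions | Ratio | Difference (points) |
|---|---|---|---|
| 5% | 14.5% v 9.75% | 1.49 | 4.75 |
| 10% | 19.0% v 14.5% | 1.31 | 4.5 |
| 20% | 28.0% v 24.0% | 1.17 | 4.0 |

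The ratio suffers much more than the difference.

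**The case against.** The strongest reply is that the plan does not ignore baseline. The same table is split by baseline class, change from baseline is tabulated at each time point (SAP 10.6.1), shift tables are planned (10.6.2), and markedly abnormal values are flagged in listings (10.6.4). Pre-existing abnormality should balance between randomised arms, and no test is specified for this table. All of that stands and limits the consequence. It does not make the headline proportion measure what its name says, and the undefined classes leave the break-down uncertain for the limits where it matters.

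Four stronger readings are tempting and are not supported:
- A reader might infer that the table mainly reports pre-existing low values. The assumed base case gives 45%, and the share exceeds half only in part of the range.
- A reader might infer that on-treatment abnormality is overstated. It is not: these women do have abnormal values on treatment. What is overstated is change.
- A reader might infer that the whole laboratory table is affected. The problem is confined to limits near normal values; it is negligible for limits such as > 3xULN.
- A reader might expect conditioning on baseline to remove chance crossings. It does not: 8.8% of women not beyond the limit at screening would still cross with no drug effect, against 14.4% counted now.

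**Conclusion.** The mismatch between endpoint name and counting rule is on the face of both documents, and the planned break-down mends it only in part. In practice it concerns limits close to normal values, chiefly haemoglobin and haematocrit. For haemoglobin, about 45% of flags would be pre-existing in the base case and 21% to 64% over the range tried. These figures rest on assumed distributions, normal and independent within-woman variation, two post-baseline samples and no allowance for exclusion criterion 12.

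The consequence is modest: a descriptive secondary safety table would be misread. The oocyte non-inferiority claim is untouched. Because the remedy is cheap and uses data already collected, it is still worth making.

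**What to change.** In SAP 10.6.3:
- Report the proportion of subjects with at least one post-baseline value (end-of-stimulation or end-of-trial) meeting the criterion, among subjects whose screening value did not meet the same criterion in the same direction.
- Define the baseline classes of the break-down as already meeting the criterion versus not.
- Show the subjects who already met it on a separate row, with their change from baseline, so that worsening in them stays visible.

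In SAP section 12, which now states that there are no deviations, declare the departure from the rule in protocol 9.7.4.

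The cost is a short SAP revision and one programming condition. The denominator will differ slightly between variables and should be printed for each. If the sponsor prefers to leave the protocol rule intact, the minimum is to define the classes as above and retitle the table as markedly abnormal values.
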